6.6 Enrollment Criteria

At screening visit:

- 6.6.1 Screening Inclusion Criteria
 - 1. Age 18 years or older
 - 2. Body Mass Index (BMI) $\leq 35 \text{ kg/m}^2$
 - 3. Diagnosis of symptomatic osteoarthritic joint in the index joint (Kellgren-Lawrence grade I to III or Guyette grade I to III) to be treated with MONOVISC injection.
 - 4. Failed conservative treatment for joint osteoarthritis.
 - 5. NRS pain ≥4 and ≤9 in the index joint.
 - 6. Subject must be willing to abstain from other treatments of the index joint for the duration of the study.
 - 7. Subject is willing to discontinue all analgesics including NSAIDs, except acetaminophen/paracetamol, at least seven days before the treatment injection and through the completion of the study.
 - 8. Subject is willing to use only acetaminophen/paracetamol (up to a maximum of 4.0 grams per day per the package insert) for the treatment of joint pain for the duration of the study. At least forty-eight hours prior to the Baseline Visit and each follow-up assessment, the subject is willing to discontinue use of acetaminophen/paracetamol.
 - 9. Subject is willing to maintain a stable dose of oral glucosamine and/or chondroitin sulfate products throughout the study, if taken prior to signing the informed consent form (ICF).
 - 10. Able and willing to provide signed informed consent.

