6.6.2 Screening Exclusion Criteria

- 1. History of hypersensitivity to any of the ingredients in the hyaluronan
- 2. Infection or skin disease in the area of the injection site or index joint
- 3. NRS pain \geq 3 in the contralateral joint
- 4. Subject received an injection of Hyaluronic Acid (HA) and/or steroid in either joint within 6 months of signing the informed consent form (ICF). A subject will be excluded if they are planning to receive an HA or steroid injection (other than the study injection) in either joint during the course of this study.
- 5. Known inflammatory or autoimmune disorders (including rheumatoid arthritis, gout), or other pre-existing medical conditions that, in the opinion of the investigator, could impact treatment of the index joint or affect the ability of the subject to accurately complete the study questionnaires and comply with the study requirements.

6. Subject is taking medications at the time of signing the ICF which could interfere with the treatment procedure, healing and/or assessments. This includes but is not limited to oral or injectable anticoagulant treatments, anti-aggregant platelet treatment, chronic opioid analgesics. Low dose aspirin used for cardiovascular protection is allowed if a stable regimen is maintained for the duration of the study.

- 7. Subjects who had an oral, intramuscular, intravenous, rectal suppository or topical (excluded in index joint only) corticosteroid within 30 days of signing the ICF are excluded. Topical corticosteroid use at any site other than the index joint is allowed.
- 8. Significant trauma to the index shoulder within 26 weeks of screening.
- 9. Chronic use of narcotics or cannabis.
- 10. Ligament instability or tear in index joint.
- 11. Diagnosis of fibromyalgia
- 12. Diagnosis of osteonecrosis in index joint
- 13. Uncontrolled diabetes with a HbA1c of >7%.
- 14. Subject is a woman who is pregnant or breastfeeding at the Screening Visit or a woman of child bearing potential who refuses to use effective contraception during the course of the study.
- 15. Subject is receiving or in litigation for worker's compensation.
- 16. Otherwise determined by the investigator to be medically unsuitable for participation in this study.

At baseline visit:

- 6.6.3 Baseline Inclusion Criteria
 - 1. NRS pain ≥4 and ≤ 9
- 6.6.4 Baseline Exclusion Criteria
 - Subject has a decrease of ≥ 2 in the NRS pain from Screening to Baseline in the index joint.

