7.3.9.4 Non-Drug Therapies

Non-drug therapies are any therapies used to treat the index joint that are not a pharmaceutical

Version 2.0 14 Aug 2019 Confidential Page 17 of 38

treatments.

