#### 4.1.3.5 Time to Treatment Failure.

The time to treatment failure will be assessed via the estimation of the Kaplan-Meier curve. This will be done via the PROC LIFEREG procedure in SAS. The estimate of the median survival time and the 95% confidence intervals will be reported. This will be done for each protocol.

For all studies, a patient is considered a treatment failure if any of the following occur:

Corticosteroid injections
Shock-wave therapy
Dry Needling
Nitroglycerin patches
Prolotherapy (PrT).
Platelet / PRP / BMAC injection
Hyaluronic Acid.
Surgical treatment – open or arthroscopic

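### The SAP's treatment-failure rule is not limited to the index joint or to the time after the study injection, so treatment given elsewhere can count as failure of the shoulder injection

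*SAP*

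**What the plan says.** Protocol 6.2 lists time to treatment failure as a secondary endpoint, and 6.3 lists treatment failure as an exploratory one. The protocol defines neither. The definition is in SAP 4.1.3.5: "For all studies, a patient is considered a treatment failure if any of the following occur". Eight interventions follow, among them "Corticosteroid injections", "Nitroglycerin patches", "Hyaluronic Acid" and "Surgical treatment – open or arthroscopic". No item carries a joint, a side, an indication or a start date. SAP 1.0 states that one plan serves the hip, shoulder and ankle studies, so the list itself does not show which joint is meant.

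The result is to be shown as a Kaplan-Meier curve, with the median and its 95% confidence interval.

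Elsewhere the documents do name the joint. The responder endpoint (SAP 3.0) is tied to the index joint. Protocol 6.6.1 item 6 reads "Subject must be willing to abstain from other treatments of the index joint for the duration of the study". Protocol 7.3.9.4 begins "Non-drug therapies are any therapies used to treat the index joint".

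**The concern.** The endpoint is meant to show how long the injected shoulder goes without needing a further intervention. Treatment of a knee or a heart condition says nothing about that, yet the rule as worded counts it.

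Such treatment can occur in this population. Protocol 6.6.2 item 4 excludes people who are "planning to receive an HA or steroid injection (other than the study injection) in either joint during the course of this study". That covers the two shoulders and planned use; it does not mention a knee or hip. Protocol 7.3.9 lets subjects continue medication for unrelated conditions if it does not interfere with study assessments. Nothing in the eligibility criteria rules out surgery at another site.

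A programmer who follows the SAP therefore has no stated ground for leaving these events out. If exclusions are decided case by case, they are decided in an open-label study with outcomes already visible.

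**Working it through.** **The plan's own figures.** The SAP gives no figure for this endpoint. Its one calculated figure, 15 subjects for the primary one-sample t-test, reproduces with a mean change of 2, SD 2.5, two-sided 5% and the noncentral t distribution (power 82.1%). The present point does not depend on it.

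**Which events could be counted.** Two conditions must hold: the event fits the wording of SAP 4.1.3.5, and it is recorded.

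| Treatment away from the index shoulder | Fits the wording? | Recorded? |
|---|---|---|
| Hyaluronic acid or corticosteroid injection in another joint | Yes | Yes, as concomitant medication (Protocol 7.3.9.3) |
| Nitroglycerin patch for another condition | Yes | Yes, same section |
| Surgery at another site | Yes | Not certain; a planned operation for an existing condition is not clearly an adverse event under Protocol 8.1.1 |
| Dry needling or shock-wave therapy elsewhere | Yes | Perhaps not; Protocol 7.3.9.4 covers the index joint only |

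The exposure is therefore mainly to the drug-type items. Protocol 7.3.9.3 collects route and indication, but the joint treated is not among its listed fields.

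**Effect of one event.** Input: 25 subjects (Protocol 9.1, SAP 4.1.1), all followed to 6 months. One counted event in a subject with no index-joint failure changes the failure proportion by 1/25 = 4.0 percentage points. With exact (Clopper-Pearson) 95% intervals:

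- 0/25 = 0% (0 to 13.7%)
- 1/25 = 4% (0.1 to 20.4%)
- 2/25 = 8% (1.0 to 26.0%)

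**How likely it is.** The documents give no rate p of such events per subject over 6 months, so p is an assumption. Expected number = 25p; chance of at least one = 1 − (1 − p)^25.

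| Assumed p | Expected number | Chance of at least one |
|---|---|---|
| 2% | 0.5 | 1 − 0.98^25 = 39.7% |
| 5% | 1.25 | 1 − 0.95^25 = 72.3% |
| 10% | 2.5 | 1 − 0.90^25 = 92.8% |

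**Effect on the reported summary.** With full follow-up the curve stands at 1 − k/25 after k failures. It is 0.52 at k = 12 and 0.48 at k = 13, so the median is reached only at the 13th failure. One or two extra events move the curve, but bring the median into view only if index-joint failures are already near half of the subjects.

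**The case against.** The strongest reply is that the intent is plain. The studies aim to relieve pain in a specified joint (SAP 3.0), the injection goes into that joint, and most readers would take failure to mean failure there. That is probably what was meant. But a SAP exists to make such rules explicit, and intent does not settle how an injection in the opposite shoulder should be handled.

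It can also be said that the endpoint is secondary, single-arm and descriptive, with no hypothesis test in 4.1.3.5, and that eligibility limits exposure: Protocol 6.6.2 items 5 and 6 exclude interfering conditions and medications. All of this stands. It reduces the consequence but does not supply the missing limit.

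A reader might infer more than the documents support:

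- **That every subject fails on day 0**, because the study injection is itself hyaluronic acid and is not excepted. Nobody would program it so. It shows only that an exception should be written in.
- **That a patch already in use at entry is a failure at time 0.** The rule speaks of something that occurs, within a time-to-event endpoint, and a treatment already under way is not naturally such an event. What stands is that the rule does not say when counting starts.
- **That every off-joint treatment will be counted.** Protocol 7.3.9.4 limits the record of non-drug therapies to the index joint, so some would never reach the data.

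**Conclusion.** The point holds as a fault in the wording of one endpoint definition. SAP 4.1.3.5 lacks both an index-joint limit and a post-injection start, and no other section of either document supplies them. Literal use would count recorded treatments that have no bearing on the injected shoulder.

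The size is 4 percentage points on the 6-month failure proportion per such event, assuming 25 subjects, full follow-up and no earlier index-joint failure in the same subject. The 40%, 72% and 93% chances of at least one event rest wholly on assumed rates of 2%, 5% and 10%.

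The effect is confined to time to treatment failure and the related exploratory endpoint. The reported median may well not change. The primary NRS analysis and the sample size are unaffected, so the point does not call the trial's main conclusion into question. It should be corrected before analysis because the correction is short and removes a discretionary decision.

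**What to change.** Reword the lead-in of SAP 4.1.3.5 along these lines: *treatment failure is dated at the first of the interventions below that is given to the index joint after the study injection*. Change the hyaluronic acid item to *hyaluronic acid other than the study injection*.

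Use *index joint*, not *index shoulder*, because the same text governs the hip and ankle studies. Do not add a restriction to osteoarthritis symptoms: it could drop a genuine intervention in the index joint that was recorded under another indication.

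List the same interventions at other sites, including the contralateral joint, in a separate table. The documents do not settle how contralateral treatment should count, so the sponsor should confirm that choice in the text.

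The cost is small but not nil. The joint treated is not among the concomitant-medication fields in Protocol 7.3.9.3, so some entries may need a data query or medical review. The change defines an endpoint only and alters no rule on treating subjects.

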#### 4.1.3.6 Reduction in Pain Medication usage at 1 Month, 3 Months and 6 Months.

The reduction from screening -baseline period in the mean reduction of medication usage per day between each visit will be tabulated and 95% confidence intervals will be calculated.

Number of subjects taking rescue medication between each visit will be tabulated.

This will be estimated using PROC MEANS. The results will tabled like the primary endpoint in section 4.1.2.1.

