7. STUDY PROCEDURES

7.1 Schedule of Events

	Screening Visit	Baseline	Month 1 Visit	Month 3 Visit	Month 6 Visit
Assessments	Day -14 to -7 days ±2 days	Visit Day 0	±3 days	± 7 days	± 7 Days
Informed Consent	Х		(M)		
Evaluation of Enrollment Criteria	х	х			
Demographics	Х				
Vital Signs	Х				
History Joint OA (Index & Contralateral for wrist, elbow and shoulder)	х				
Medical History	х				
Concomitant Medication	х	х	X	х	х
Assess non-drug therapies	х	х	Х	Х	Х
Adverse Event Assessment		Х	X	Х	Х
Collect & Review Subject Diary		Х	X	Х	х
Rescue Medication usage / washout		х	X	х	х
Patient Global Assessment (PGA)	Х	Х	X	х	х
DASH index index shoulder	Х	Х	X	Х	Х
Index and Contralateral Shoulder Joints Pain (0-10 Numeric Rating Scale)	х	х	х	х	x
Physical Evaluation of Index and Contralateral Shoulder Joints	х	x	х	Х	X
Study Injection		х			
Dispense Subject Diary		х			

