7.2 Procedure Description

7.3 Screening Visit (Day -14 to -2 days)

The following screening and eligibility data will be collected.

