7.3.9.2 Rescue Medications

Acetaminophen/paracetamol (up to a maximum of 4.0 grams per day per the package insert or as per regional limitations) will be allowed as the rescue medication for the treatment of Osteoarthritis for the duration of the study. At least forty-eight hours prior to the Baseline Visit, 1, 3 and 6 Month Assessments the subject should discontinue use of the rescue medication.

The subject should be instructed to track pill usage daily to convey accurate pill counts at follow-up assessments.

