7.4 Baseline Visit: Treatment Visit (Day 0)

The Baseline Visit (Day 0) will occur 7 to 14 days after the Screening Visit to allow for rescue medication washout. The injection will occur at this Baseline visit along with the following activities:

Before Treatment Injection

- Concomitant Medications
- Current non-drug therapies
- Confirm Medication Washout
 - If subject did not complete medications washout, reschedule the visit to allow washout to be completed.
- Patient Global Assessment (PGA)
- DASH index shoulder
- Index & Contralateral Shoulder Joint Pain (NRS Scale)
 - o Confirm Baseline Inclusion & Exclusion Criteria for NRS pain
- Physical Exam of Index and Contralateral Shoulder Joints

Treatment Procedure

The Treating Physician will always perform the Study Injection to the index joint as standard of care dictates.

Intra-articular injection of the shoulder joint should be conducted under fluoroscopic or ultrasound guidance. Guidelines for the injection procedural steps are provided below. Modifications to this technique should be recorded in the CRF

- Patient may be sitting or supine as required.
- Prep the skin at injection site with 1% betadine solution or equivalent.
- Peri- articular injection site anesthesia of lidocaine or topical refrigerant anesthetic (e.g. ethyl

chloride) may be utilized.

- Use fluoroscopic or ultrasound guidance to insert 18-22 1 cm lateral and 1 cm cephalad to the coracoid process. Insert the needle directed 20° medially and 60° caudally to enter the joint.
- Insert needle until resistance against the articular surface and then withdraw the needle 1-2 mm.
- If using fluoroscopic guidance, a small amount of fluoroscopic contrast agent (0.5 to 1.0 ml) should be injected through the needle to verify intra-articular placement.
- If using ultrasound guidance, a small volume of air (up to 0.5 ml) may be injected to verify IA positioning.
- If pooling of the contrast agent or air around the needle tip is observed, the needle should be repositioned.
- When contrast agent or air is successfully injected into the joint, intra-articular placement is confirmed.
- Following confirmation of intra-articular needle placement, the joint may be aspirated to remove synovial fluid.
 - o Confirm the Baseline Exclusion for synovial aspirate.
- 4 ml of MONOVISC is injected into the joint.
- Intra-articular anesthetic should NOT be administered as part of the injection procedure.

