7.5 Follow-Up Visits

All study subjects will have follow-up visits at 1, 3 and 6 Months after Baseline to evaluate the joint pain score and to assess adverse events.

The subject should be contacted at least 48 hours prior to their scheduled assessments to be reminded of the required assessment (and applicable wash out period) and to schedule the date and time of contact. At least three documented attempts will be made to contact the subject in order to accomplish maximum subject compliance with the follow-up schedule.

The following tests will be performed at the follow-up visits at 1, 3, and 6 months.

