7.6 Follow-up Visits (± 7 days)

- Assess Concomitant Medications
- Assess Non- drug therapies
- Assessment of Adverse Events
- Assess Rescue Medication usage
- Confirm Rescue Medication Washout
 - If subject did not complete medications washout, reschedule the visit to allow washout to be completed.
- Collect and assess subject diary
- Patient Global Assessment (PGA)
- DASH index shoulder
- Index & Contralateral Shoulder Joint Pain (NRS)
- Physical Exam of Index and Contralateral Shoulder Joints

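### SAP 4.1.3.6 has no rule for washout days, so on its plain reading it understates any reduction in rescue acetaminophen/paracetamol use

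*SAP*

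**What the plan says.** Reduction in medication use is a listed secondary endpoint (Protocol 6.2; SAP 3.0). SAP 4.1.3.6 states: "The reduction from screening -baseline period in the mean reduction of medication usage per day between each visit will be tabulated", with 95% confidence intervals. The sentence is awkward. I read it as the change in mean daily use from the screening-baseline period to each later inter-visit period. It does not define the day count, does not mention washout, and does not say which pain medications enter the mean.

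Protocol 7.3.9.2 allows acetaminophen/paracetamol as rescue throughout, with one restriction: "At least forty-eight hours prior to the Baseline Visit, 1, 3 and 6 Month Assessments the subject should discontinue use of the rescue medication". The check is built into the visits. Protocol 7.6 lists "Confirm Rescue Medication Washout", and both 7.4 and 7.6 reschedule the visit if washout is incomplete.

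The length of the reference period is given in three ways:
- Protocol 7.4: "The Baseline Visit (Day 0) will occur 7 to 14 days after the Screening Visit to allow for rescue medication washout".
- Protocol 7.1, Schedule of Events: "Day -14 to -7 days ±2 days".
- Protocol 7.3, heading: "Screening Visit (Day -14 to -2 days".

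Other analgesics follow a different rule (Protocol 6.6.1): "Subject is willing to discontinue all analgesics including NSAIDs, except acetaminophen/paracetamol, at least seven days before the treatment injection".

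**The concern.** Each period, including the reference, ends with a block of required zero rescue use. The block is about the same length every time, but the periods are not: one to two weeks for the reference, then roughly one, two and three months. A mean over all days is therefore pulled down much more in the reference than in follow-up.

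The study has one arm, so no control group cancels the difference. A larger sample would not remove it either, because it is systematic. It also varies with each subject's screening length. The reported change and its confidence interval for this endpoint are shifted, and a modest true reduction could be tabulated as an increase.

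**Working it through.** The documents give no figure for this endpoint, so there is none to reproduce.

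**Inputs**
- Washout: at least 48 hours per visit (Protocol 7.3.9.2), taken as exactly 2 days.
- Reference length: 7 to 14 days (Protocol 7.4).
- Follow-up intervals: visits at 1, 3 and 6 months (Protocol 7.5). Lengths of 30, 61 and 91 days are my assumption.
- Use on permitted days: assumed constant within a period, r0 in the reference and r1 in follow-up.

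**Formulas.** For a period of L days, the abstinent share is w = 2/L and the permitted share is 1 − w. Measured use per day is r(1 − w).
- Measured absolute reduction = r0(1 − w0) − r1(1 − w1).
- Measured relative change = (r1/r0) × (1 − w1)/(1 − w0) − 1.

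**Abstinent shares.** Reference: 2/7 = 28.6%, 2/14 = 14.3%. Follow-up: 2/30 = 6.7%, 2/61 = 3.3%, 2/91 = 2.2%.

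**Permitted shares.** Reference: 5/7 = 0.714, 12/14 = 0.857. Follow-up: 28/30 = 0.933, 59/61 = 0.967, 89/91 = 0.978.

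**Unchanged use (r1 = r0).** The absolute rise is in units/day per unit used per permitted day.

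| Reference | Measure | 30 d | 61 d | 91 d |
|---|---|---|---|---|
| 7 days | absolute rise | 0.219 | 0.253 | 0.264 |
| 7 days | relative | +30.7% | +35.4% | +36.9% |
| 14 days | absolute rise | 0.076 | 0.110 | 0.121 |
| 14 days | relative | +8.9% | +12.8% | +14.1% |

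**Visit windows.** Protocol 7.1 gives ±3 days at Month 1, but the heading of 7.6 gives ±7 days. With ±7 the first interval can be 30 − 7 = 23 days, with share 21/23 = 0.913. The lower limits become 0.913/0.714 − 1 = +27.8% and 0.913/0.857 − 1 = +6.5%. The longest last interval, 105 days (share 103/105 = 0.981), gives +37.3% and +14.4%.

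**True 20% fall, last interval.** 0.8 × 0.978/0.714 − 1 = +9.5% (7-day); 0.8 × 0.978/0.857 − 1 = −8.7% (14-day). The sign depends only on screening length.

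**True 50% fall.** It shows as 31.5% to 34.7% (7-day) or 42.9% to 45.6% (14-day).

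**Full stop (r1 = 0).** The absolute reduction shows as 0.714 r0 or 0.857 r0 instead of r0, an understatement of 28.6% or 14.3%. The relative change is still −100%.

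**Direction.** The true reduction minus the measured one is w0·r0 − w1·r1. With w0 > w1 and r1 ≤ r0 this is always positive, so every reduction is understated on the absolute scale.

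**Other screening windows.** If ±2 days applies to both ends of the range in 7.1, the reference is 5 to 16 days: unchanged use shows +56% to +63% at 5 days and +7% to +12% at 16 days. A 2-day reference under the 7.3 heading has no permitted day.

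**Other analgesics.** Suppose they are counted in the same units and taken on the first 7 days of a 14-day reference. The rate, as a fraction of the daily rescue rate, that cancels the effect is (14 × follow-up share − 12)/7 = 0.152, 0.220 and 0.242 for the three intervals. Higher use reverses it.

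**The case against.** The strongest objection is that the SAP never says calendar days. A reader might infer that it prescribes averaging over washout days; it does not. That is the plain reading of use per day between visits, and an analyst who left those days out would avoid the bias. This stands as a limit on the claim. But nothing in either document tells the analyst to leave them out, and the choice can change the sign of the result.

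Second, the heading of SAP 4.1.3.6 refers to pain medication, while rescue medication appears only in a separate count of users. If the mean covers all analgesics, use before their required stop can cancel or reverse the effect, as the 0.15 to 0.24 figures show. This also stands: the direction holds only for acetaminophen/paracetamol.

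Third, it is unclear whether daily use in the reference period is recorded at all. Protocol 7.1 both dispenses and collects the diary at Baseline and dispenses it at no other visit. Protocol 7.3.9.6 says subjects receive a diary but not when. This stands and belongs in the fix.

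Finally, for rescue medication the error works against the product and touches one secondary endpoint. That is a fair argument for minor severity, not for leaving the rule unwritten.

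**Conclusion.** The concern holds for rescue acetaminophen/paracetamol on the plain reading of SAP 4.1.3.6. Unchanged use on permitted days would be tabulated as a rise of 0.22 to 0.26 (7-day reference) or 0.08 to 0.12 (14-day) units/day per unit used per permitted day. In relative terms that is +31% to +37% or +9% to +14%, with lower limits of +27.8% and +6.5% if ±7 days applies at Month 1. Any reduction is understated on the planned absolute scale, a full stop included; only in relative terms is a full stop unaffected.

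These sizes assume compliance, exactly 48 hours of washout, constant use on permitted days and intervals of 30, 61 and 91 days. The protocol says at least 48 hours, and longer washout enlarges the effect.

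Two stronger inferences are not supported. The bias cannot create a false benefit for rescue medication, because it is conservative there. It also does not reach the primary endpoint or the sample size, which rest on NRS pain. Severity: minor.

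**What to change.** **SAP 4.1.3.6**
- Define the measure as the amount of acetaminophen/paracetamol per permitted day. In every period, including the reference, exclude the 48 hours before the visit (Baseline included) from both numerator and denominator.
- Take both from the daily record. Protocol 7.3.9.2 already asks for daily tracking. A pill total alone cannot remove a pill taken inside the window.
- Keep days of voluntary non-use outside the window in the denominator, so that they still count as benefit. Illustration: the reference is 2 pills per permitted day; in the last interval the subject takes 2 a day for 45 days and none for 46. Excluding 48 hours gives 90/89 = 1.01, a 49% reduction. Excluding all 46 non-use days gives 90/45 = 2.0, a 0% reduction.
- Set no reference value when the reference period has no permitted day.
- Tabulate other analgesics separately.

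**Protocol**
- Reconcile the screening windows in 7.1, 7.3 and 7.4.
- Reconcile diary dispensing and collection in 7.1 with 7.3.9.6, so that reference-period use is captured.

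With exactly 48 hours of washout the permitted share cancels, and a true 50% fall reads as 50% for any reference length with a permitted day. The rule is not perfect. If washout actually lasts 3 days, unchanged use still shows +20.5% to +23.6% (7-day: for example (27/28)/(4/5) − 1 = +20.5%) or +5.2% to +7.9% (14-day). Recording an individual washout start at each visit is more than this endpoint needs, and the reminder contact in Protocol 7.5 is described only for follow-up visits, not Baseline.

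The cost is SAP wording, a corrected schedule and slightly more data handling. There are no new visits, and what patients may take does not change.

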6. ENDPOINTS

6.1 Primary Endpoint:

Reduction of index joint Numerical Rating Scale (NRS) pain from baseline to 6 Months post injection.

6.2 Secondary Endpoints:

- Improvement in DASH index joint from baseline to 6 months post injection.
- Improvement in Patient Global Assessment (PGA) from baseline to 6 months post injection.
- OMERACT-OARSI responder rate in the index joint at 6 months post injection.
- Time to treatment failure
- Reduction in Medication usage from baseline to 6 months post injection.

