6.3 Exploratory Endpoints

Any comparisons across timepoints (baseline to 6 months) not described in the primary or

Version 2.0 14 Aug 2019 Confidential Page 11 of 38

MON 18-02

secondary endpoints, including but not limited to:

- Demographics
- Medical History
- History of joint osteoarthritis
- Rescue Medication Use
- Treatment Failure
- Injection procedure
- Concomitant medications
- Non-drug therapy.

6.4 Safety Endpoint:

The incidence, severity, and relationship to treatment of all Adverse Events (AE) will be collected from the treatment injection to the 6 month assessment.

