7.3.9.1 Restricted Medications

All analgesics other than acetaminophen/paracetamol are prohibited during the study. This includes, but is not restricted to, NSAIDs, opioids and topical agents for treatment of osteoarthritis of index joint. Topical corticosteroids are allowed at any other site other than the index joint. The analgesic medication use will be monitored at each subject assessment through review of the subject diary.

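### The reference period for the pain-medication endpoint can include days under a looser analgesic rule than follow-up, so part of the reported change may be unrelated to the injection

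*SAP*

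**What the plan says.** The protocol (section 6.2) lists as a secondary endpoint: "Reduction in Medication usage from baseline to 6 months post injection". It gives no drug class, unit or reference window.

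SAP 4.1.3.6, whose heading refers to pain medication, supplies the reference: "The reduction from screening -baseline period in the mean reduction of medication usage per day between each visit will be tabulated". The sentence mentions reduction twice. I read it as use per day between Screening and Baseline minus use per day in each follow-up interval. The same section adds "Number of subjects taking rescue medication between each visit will be tabulated".

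Two protocol passages govern analgesics other than paracetamol. Criterion 7 of section 6.6.1 reads "Subject is willing to discontinue all analgesics including NSAIDs, except acetaminophen/paracetamol, at least seven days before the treatment injection" and runs to study completion. Section 7.3.9.1 states "All analgesics other than acetaminophen/paracetamol are prohibited during the study" and gives no start date.

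On the length of the reference period, section 7.4 says "The Baseline Visit (Day 0) will occur 7 to 14 days after the Screening Visit to allow for rescue medication washout". The schedule in 7.1 gives Day -14 to -7 with a tolerance of two days, and the heading of 7.3 gives Day -14 to -2. Section 7.3.9.2 requires paracetamol to be stopped at least 48 hours before Baseline and before each follow-up assessment.

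**The concern.** A change from a reference period is interpretable only if the same background rule applies in both periods. After injection, paracetamol is the only analgesic allowed. Before injection, criterion 7 fixes only the latest stopping point, Day -7. A subject screened at Day -14 may take an NSAID for the first week of the reference period and still comply.

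The effect depends on what is counted, and neither document says. If all pain medication counts, stopping the NSAID lowers use whatever the injection does. If only paracetamol counts, NSAID cover early in the reference may hold down paracetamol use there, so follow-up looks worse by comparison. The study is single-arm and open-label, so no concurrent group would show either artefact. At stake is a secondary efficacy result reported with a 95% confidence interval.

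**Working it through.** The documents give no figure for this endpoint, so there is none to reproduce.

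**Inputs from the documents**
- Reference length L: 7 to 14 days (Protocol 7.4), up to 16 with the tolerance in 7.1.
- Latest stop for other analgesics: Day -7 (6.6.1, criterion 7).
- Paracetamol washout: 2 days before Baseline and before each follow-up assessment (7.3.9.2).

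**Assumptions, for illustration only**
- Constant daily use, NSAID stopped exactly at Day -7, none afterwards, no treatment effect.
- Follow-up intervals F of 30, 61 and 91 days.

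**Step 1. Share of the reference in which NSAIDs may be allowed:** (L − 7)/L, or 0 if L is 7 or less.

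**Step 2. All analgesics counted.** With a twice-daily NSAID and no paracetamol, the apparent reduction is 2 × (L − 7)/L.

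| L (days) | Share | Apparent reduction, doses/day |
|---|---|---|
| 7 | 0% | 0 |
| 8 | 1/8 = 12.5% | 0.25 |
| 10 | 3/10 = 30% | 0.6 |
| 14 | 7/14 = 50% | 1.0 |

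At L = 16 the share is 9/16 = 56%.

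**Step 3. Paracetamol only.** Take a subject who uses no paracetamol while on the NSAID and 2 doses/day on permitted days afterwards. The reference holds 5 such days (7 minus 2 washout days), or 10 doses.
- L = 14: reference 10/14 = 0.71; first follow-up interval 2 × 28/30 = 1.87; apparent increase 1.15 doses/day.
- L = 7: reference 10/7 = 1.43; apparent increase 0.44 doses/day, all of it from washout.

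**Step 4. Weight of the washout.** It takes 2/7 = 28.6% of a 7-day reference and 2/14 = 14.3% of a 14-day one. In follow-up it takes 2/30 = 6.7%, 2/61 = 3.3% and 2/91 = 2.2%.

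**Step 5. Both effects, all analgesics counted.** With 1 NSAID and 2 paracetamol doses/day, the apparent reduction at 1 month is (L − 7)/L + 2(L − 2)/L − 2 × 28/30.
- L = 7: 0 + 1.43 − 1.87 = −0.44
- L = 10: 0.30 + 1.60 − 1.87 = +0.03
- L = 14: 0.50 + 1.71 − 1.87 = +0.35

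The sign changes with the screening interval alone.

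**Step 6. Check of the remedy.** Apply it to the subject in Step 3: paracetamol only, days after the NSAID stop, washout days removed from numerator and denominator. The reference is 10/5 = 2.0 and the first follow-up interval 56/28 = 2.0. The change is 0, as it should be when nothing has changed.

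**The case against.** The strongest reply is that the reference is mostly or wholly under the same ban as follow-up. With a 7 to 14 day interval, at least 7 days fall after the latest permitted stop. If the prohibition in 7.3.9.1 runs from consent, the whole period is covered and a compliant subject has no NSAID days in it. There are also signs that rescue paracetamol is what is meant. It is the only medication type SAP 4.1.3.6 names, Protocol 7.3.9.2 asks for daily pill tracking for it, and a per-day count suits one drug better than a mixture with no common unit. Finally, the endpoint is one of several secondary ones and has no stated hypothesis test.

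Much of this stands. A reader might infer that NSAIDs are allowed throughout the reference period, or that the protocol creates a reduction in every compliant subject. The documents support neither. The artefact is zero for subjects who take no NSAID, who stop at or before Screening, or who are screened at Day -7. The washout pushes the other way.

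It does not remove the problem. Criterion 7 names a date and 7.3.9.1 does not, so the documents leave it open whether the first part of the period is covered. The drug set is also unsettled: the SAP heading is broader than rescue medication, and "Rescue Medication Use" is listed separately as exploratory, although the SAP's detailed exploratory section omits it. Choosing paracetamol only does not by itself make the periods comparable, as Step 3 shows.

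**Conclusion.** The concern holds in conditional form. When Screening is more than seven days before injection and criterion 7 sets the stop, up to 7 of 14 reference days (9 of 16 with the schedule tolerance) can follow a different analgesic rule from follow-up. For the assumed twice-daily NSAID user, counting all analgesics gives a spurious reduction of 0 to 1.0 dose/day over reference lengths of 7 to 14 days. Counting paracetamol alone can give a spurious increase. The net sign is not fixed.

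These sizes rest on assumed doses. A reader might go further and expect the 95% confidence interval to exclude zero for an inert injection. The documents give neither the proportion of NSAID users nor their doses, so that cannot be claimed. What can be said is that the stated reference rule does not ensure a comparable baseline under either definition of medication use. For a secondary endpoint, this should be corrected before analysis.

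**What to change.** In SAP 4.1.3.6:
- Define the endpoint as paracetamol use per day and state the unit.
- Take the reference only from screening-to-baseline days after other analgesics were stopped.
- Exclude the 48-hour washout days from numerator and denominator, in the reference and in every follow-up interval. Without this, shortening the reference to about 7 days makes the washout imbalance worse (2/7 against 2/30).
- Tabulate use of prohibited analgesics after injection separately, as number and percent of subjects.

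In the protocol, reconcile criterion 7 with 7.3.9.1 on when the ban starts, and reconcile the screening windows in 7.1, 7.3 and 7.4. Correct the schedule too: it dispenses the diary only at Baseline yet collects it at Baseline, so daily use in the reference period may not be recorded as it happens.

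The SAP part costs wording and derivation code. Start and stop dates, dose and frequency are collected from consent (7.3.9.3), but these are not daily counts, so the diary correction matters. The price is a shorter, noisier reference: about 7 − 2 = 5 usable days for a subject who stops other analgesics at Day -7.
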